**CODE CLINICAL TRIALS NCT03204890**

**JUNE 2017**

## **ABSTRACT**

**Background:** Transcutaneous posterior tibial nerve stimulation is an effective therapy for controlling urinary incontinence. Premature ejaculation (PE) and urinary incontinence are anatomically and physio-pathologically similar. Based on this, the use of this therapy is considered to be viable for the control of PE.

**Objective:** To evaluate the efficacy of transcutaneous posterior tibial nerve electrostimulation for the ejaculatory reflex.

**Patients and Methods:** Phase II clinical trial. Patients with a diagnosis of premature ejaculation who are treated at the Colombia Boston Medical Group clinic will be included. The participants will receive 3 transcutaneous posterior tibial nerve stimulation therapies per week for 12 weeks. The IELT and the PEDT scale will be evaluated on week 6, at the end of treatment and three months after completing the protocol.

**Expected Impact:** Generate scientific knowledge about the efficacy of a new option to treat premature ejaculation, which can subsequently be compared with current treatments.

## INTRODUCTION

Premature ejaculation is a male sexual dysfunction defined by the WHO as “an inability to delay ejaculation sufficiently to enjoy intercourse,” and defined by the ISSM as “ejaculation which always or nearly always occurs prior to or within one minute of vaginal penetration, which the patient is unable to control and which causes distress or depression in the patient or the partner.” This sexual health problem affects a large number of men, with a total prevalence of 22.7% (1).

Different treatment modalities exist for this condition. According to the European Urology Society’s guide for treating sexual dysfunctions, the principal treatment is medication that regulates the reuptake of neurotransmitters such as serotonin, in addition to behavioral and psychological therapy.

Transcutaneous posterior tibial nerve stimulation is a therapy which pelvic-perineal therapists have recently used to treat a variety of pelvic floor disorders, including urge urinary incontinence and chronic pelvic pain. Favorable results have been observed and this can be used as an alternative when medications are not effective. (2,3)

Based on the results from neuro-stimulation of the posterior tibial nerve for a variety of pelvic pathologies (4,6), and given the physiology and neuroanatomy of these structures, the use of this therapy for patients with premature ejaculation may inhibit the parasympathetic function of this reflex, which primarily affects the expulsion stage of ejaculation. In addition, since these stages are regulated by the autonomic nervous system and are linked with it, the sympathetic effect of emission could also be affected by producing a global delay in the start of the ejaculatory reflex.

Our research is therefore interested in identifying whether the application of this therapeutic modality has beneficial effects on the treatment of primary premature ejaculation, where delaying intravaginal ejaculation latency time (IELT) is an indicator of the success of the proposed treatment and protocol.

## THEORETICAL FRAMEWORK

The diagnosis of premature ejaculation is entirely clinical and depends on the ability of the clinician to determine whether the criteria are met, based on different definitions that exist for the study of this dysfunction. Some of the most important are:

### **1- DSM 5 Diagnostic and Statistical Manual by the American Psychiatric Society:**

**A-** A persistent or recurrent pattern of ejaculation occurring during partnered sexual activity within approximately one minute following vaginal penetration and before the person wishes it.

**B-** The symptoms in criterion A have been present for at least six months and experienced on almost all or all (approximately 75% to 100 %) occasions of sexual activity.

**C-** The symptoms in criterion A produce clinically significant distress in the individual.

**D-** The sexual dysfunction is not better explained by a non-sexual mental disorder or as a consequence of severe relationship distress or other significant stressors and is not attributable to the effects of a substance/medication or another medical condition.

**2-American Urology Association:**

Ejaculation that occurs before or shortly after penetration, causing distress to either one or both partners.

**3-WHO (World Health Organization):**

Inability to delay ejaculation sufficiently to enjoy sexual intercourse.

**4-International Society of Sexual Medicine**

Ejaculation occurring prior to or within one minute of vaginal penetration, and the inability to delay ejaculation on all or nearly all vaginal penetrations, and negative personal consequences.

Premature ejaculation can be classified as primary or secondary. In the former, ejaculation always or nearly always occurs around one minute after vaginal penetration or sooner, it has a genetic origin (7) and is caused by changes in the levels of diverse neurotransmitters in the central nervous system, serotonin in particular (8,9). It is present since the beginning of sexual life. Secondary premature ejaculation appears after having had satisfactory sexual performance for several years.

Current treatment for premature ejaculation is primarily based on its physiopathology at the level of the nervous system, with regulation of serotonin levels being the primary objective. To this end, certain groups of medications are used that act on the central nervous system by increasing serotonin in certain receptors that regulate the ejaculatory reflex. Thus, the most commonly used medications are tricyclic antidepressants and selective and non-selective inhibitors of serotonin uptake. These have shown good results which multiple studies have confirmed for over several years. Those most commonly used are Clomipramine, Paroxetine, Sertraline and Dapoxetine. (10,11)

Another group of medications used with good results is opioid analgesics, such as Tramadol, that act on serotonin receptors and also have an effect on the beta-endorphin receptors. Nevertheless, the risk of dependency when taken chronically limits their use to short time periods.(11) Medications that function as topical anesthetics, such as combinations of lidocaine and prilocaine or s-cream, are also approved for the use of premature ejaculation. Nonetheless, since they have a high transfer rate the use of prophylactics is recommended. (11,12)

Finally, sexual education is provided by psychosexual therapy in order to dispel sexual myths, acquire confidence, control anxiety and reeducate behaviors related to sexual relations. The different therapies have shown good results, although they are much more effective when pharmacological and psychological therapies are combined. (13,14)

## Neuromodulation of the posterior tibial nerve

Peripheral neuromodulation is defined as any technique aimed at indirectly stimulating the neurological roots responsible for the motor and/or sensorial functioning of a particular organ, viscera and/or support structures. Neuromodulation of the posterior tibial nerve arose from the advances in these techniques. It has typically been performed by using a needle electrode to electrically stimulate the posterior tibial point, though a surface electrode can be used as an alternative technique. (15)

Neuromodulation of the posterior tibial and the pudendal nerves is primarily described for the treatment of pelvic floor pathologies, and neuromodulation of the posterior tibial is approved by the FDA to treat urinary incontinence when physiotherapeutic or pharmacological treatments are insufficient. (16,17)

At the physiological and anatomical levels, the micturition and ejaculatory reflexes share areas in common, which are described below. In the case of micturition, the *parasympathetic reflex arc* is the basis of this process. The detrusor muscle and the free nerve endings are stimulated by the distention of the bladder. When it fills with urine, the sensation passes through the pelvic nerve (sacral roots S2-S3 and S4) and then ascends through the medulla until reaching the neuron in the pontine micturition center (PMC) and the cerebral cortex, where the proprioceptive stimulus is converted into the desire to urinate. This can be inhibited in the brain, the basal ganglia, and the cortex itself which acts retrogradely on the PMC. This *parasympathetic reflex arc* descends until reaching the motor neuron at the sacral level (S2-S3 and S4) where it exits through the pelvic nerve until it reaches the bladder's perivesical and intramural parasympathetic ganglia, initiating the contraction of the detrusor muscle and producing micturition. The sympathetic micturition reflex arc is mediated by the hypogastric nerve which contains sensitive fibers that extend to the medulla at the level D9 to L1 and exit through the same hypogastric nerves, reaching the bladder and the urethra and producing the relaxation of the bladder's detrusor muscle and the contraction of the vesical neck, preventing micturition.

With regard to ejaculation, this has a neurological control which also depends on the synchrony of the sympathetic and parasympathetic systems, and which participate in this process synergistically. For study purposes, ejaculation is divided into two stages: emission and expulsion.

The emission stage is characterized by the mixing of fluids from the seminal glands, the prostate and the bulbourethral glands. These fluids accumulate in the prostatic urethra since the system of internal and external sphincters are closed, creating a high pressure chamber. This stage is regulated by the lumbar dorsal (D12-L2) sympathetic system. The expulsion stage is characterized by an increase in pressure in the chamber behind the prostatic urethra. This increased pressure from the rhythmic contractions of the perineal muscles, and from the urethra itself, produces the expulsion of the fluids accumulated there. This stage is controlled by the *sacral parasympathetic system* (S2-S3 and S4).

The stimuli produced in the genital area also ascend through the medulla until reaching the regions of the thalamus and the cerebral cortex where the reflex is regulated, and where the

neurotransmitters play a key role, particularly in serotonin levels, among many other functions. (18)

The posterior tibial nerve is a mixed (sensor and motor) nerve. It contains fibers that have medullary origins in the sacral plexus, as does the innervation of the structures of the pelvic floor. Thus our hypothesis is that retrogradely stimulating it with TPTNS (Transcutaneous Posterior Tibial Nerve Stimulation) will have an effect on the anatomical structures that depend on it, such as the musculature of the pelvic floor and its neighboring structures, the urethra, prostate and seminal glands. The stimulation of the posterior tibial nerve produces the inhibition of the parasympathetic stimulus, thereby affecting ejaculation.

### **Evidence Related to Posterior Tibial Neuromodulation for Urinary Incontinence and Pelvic Pain**

A variety of studies have evaluated the efficacy and safety of neuromodulation of the posterior tibial to treat urinary incontinence and pelvic pain. Four systematic reviews of this technology have been found. Since they repeated studies and results, the most recent and best quality studies are presented below.

In a systematic review published in 2012 of two randomized clinical studies with high-quality methodologies, a significant decrease in urinary frequency and urge urinary incontinence was demonstrated in patients treated with electrostimulation of the posterior tibial, compared to a placebo group. One of these studies also reported significant improvement in nocturia and urinary urgency. In another clinical trial with a high-quality methodology, no differences were observed in urinary frequency when comparing electrostimulation and Tolterodine. (19)

Bieman et. al. evaluated the effectiveness of electrostimulation for different indications, including urinary incontinence, fecal incontinence and chronic abdominal pain. This review found 5 randomized clinical trials, with small sample sizes and poor methodological quality, that suggested improvements in the symptoms associated with hyperactive bladder, frequency, urgency, nocturia and urinary incontinence (range 36.7 - 80%). With regard to symptoms related to fecal incontinence, another study included in this review found a 53% decrease for the patients who were included. And to treat pain, another clinical trial reported that chronic pelvic pain decreased in 40% of patients. None of the studies reported serious adverse events. (20)

The most recent and long-term findings from a clinical trial show favorable results with respect to frequency, episodes of urge incontinence, nocturia and episodes of moderate to severe urgency 5, 12, 18 and 24 months after finishing treatment. (21)

## JUSTIFICATION

Premature ejaculation is a condition which affects roughly 25% of the male population, creating problems in their sexual life and affecting their quality of life. (1)

Although a variety of pharmacological and therapeutic treatments exist today, they have several drawbacks that limit their long-term use, such as: undesirable secondary effects from tricyclic antidepressants and selective and non-selective serotonin reuptake inhibitors, risk of dependence with the chronic use of opioid analgesics and a high transfer rate with topical anesthetics which requires the use of condoms. (10-12)

Given the results obtained from using posterior tibial neurostimulation for several pelvic pathologies, including urge incontinence and some reported cases of chronic pelvic pain, and considering the physiology and anatomy of these structures, it is feasible that the use of this therapy for patients with primary premature ejaculation will have beneficial effects. There are three reasons for this: 1) The parasympathetic reflex is inhibited, primarily affecting the expulsion stage of ejaculation; 2) Since these stages are regulated by the autonomic nervous system and are linked with it, a sympathetic effect on emission could be achieved, generating a global delay in the start of the ejaculatory reflex; 3) Since ejaculation is also controlled at the supraspinal level, and considering studies of urinary incontinence performed by Finazzi-Agro (22) which show evidence of changes in evoked potential produced at the frontal cortex level after stimulating the posterior tibial nerve, suggesting changes at the cortex level and explaining the long-term control of incontinence, if our hypothesis is correct we could expect to see a change not only during the percutaneous electrostimulation of the posterior tibial nerve but it could also be prolonged over time.

The present study will make it possible to identify whether neurostimulation of the posterior tibial is beneficial for patients with premature ejaculation, as well as to determine the risks associated with this therapy. This evidence will serve as a basis for subsequent comparative studies to evaluate the best treatment options, thereby providing an opportunity to offer patients more treatment options, possibilities and alternatives to complement or substitute current treatments.

## OBJECTIVES

### Primary

Evaluate the efficacy of transcutaneous electrostimulation of the posterior tibial nerve on the ejaculatory reflex.

### Secondary

- Measure changes in ejaculation time during and after the stimulation of the posterior tibial nerve, based on the PEDT (Premature Ejaculation Diagnostic Tool) and IELT (intravaginal ejaculation latency time).
- Evaluate the secondary or adverse effects of this therapy on the quality of the erection using the IIFE5 and EHS.
- Quantify secondary or adverse sexual effects from transcutaneous posterior tibial nerve stimulation.
- Determine the appropriate therapy time for the administration of posterior tibial electrostimulation for ejaculation control.

## RESEARCH HYPOTHESIS

**Null hypothesis:** No clinically significant improvement in ejaculation time exists for patients who are treated with Transcutaneous Posterior Tibial Nerve Stimulation (TPTNS)

**Alternative hypothesis:** Clinically significant improvement in ejaculation time exists for patients who are treated with Transcutaneous Posterior Tibial Nerve Stimulation (TPTNS).

## **MATERIALS AND METHODS**

### **Type of Study**

Phase II Clinical Trial

### **Study Population**

Patients who have been admitted to the Boston Medical Group clinics in Bogota and have been diagnosed with primary premature ejaculation and have not received treatment over the last six months.

### **Sample**

Patients in the study population who meet the following selection criteria:

#### **Inclusion criteria**

- Over 18 years of age and less than 50 years of age with no cardiovascular risk factor other than age.
- Having been diagnosed with primary premature ejaculation according to the American Psychiatric Society's DSM 5 Diagnostic and Statistical Manual.
- Agreeing to participate and providing signed informed consent.
- Stable relationship for over 6 months, with frequent intercourse at least once per week.

#### **Exclusion criteria:**

- Diagnosis of erectile dysfunction according to the IIFE 5 (score under 21).
- A PEDT score under 8.
- Use of treatment for premature ejaculation during the study or over the 6 months prior to beginning the study.
- Use of pacemaker or heart defibrillator.
- Epilepsy or convulsions
- Venous insufficiency (varices) or cutaneous wounds or injuries on the lower extremities.
- Congenital or acquired anatomical abnormalities of the penis.
- Taking medications that affect ejaculation control, including psychiatric medications, opioid analgesics and medications for pathologies of the prostate such as alpha blockers.
- Psychological or psychiatric disorders that prevent the patient from undergoing the treatment or recording the measurements as established.
- Difficulty going to the clinic 3 times per week as required by the protocol.
- Patients with precoital premature ejaculation.
- Use of barrier contraceptive methods or local anesthetics.

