#### **Sample size**

The "single stage procedure" proposed by Fleming was used to estimate the sample size for this type of trial. For  $P_0=10\%$  and  $P_1=30\%$  with an alpha error of 5% and a beta of 80%, 18 patients need to be included in order to prove the study's hypothesis. After adjusting this number by a percentage of loss of 30%, which is observed in daily practice, 24 patients will be included in the study.

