## OUTCOMES

### Primary Outcome

Proportion of patients with clinical improvement of premature ejaculation, defined as a tripling of the baseline time (without treatment), as measured by the IELT (intravaginal ejaculation latency time) during the therapy and three months after completion.

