## OUTCOME VARIABLES

Since the aim is to evaluate possible changes in the length of time of the appearance of the ejaculatory reflex, two tools will be used to quantify this datum: the PDET and IELT (Appendix 1). The first is a questionnaire that evaluates the perception the patient has of his situation, and the second will be measured with a timer which the patient will use to document the time it takes between vaginal penetration and the appearance of ejaculation, data which must be recorded on the in-home chart (Appendix 2) which each patient will have and which he must bring to each follow-up appointment. These data will be used to quantify the following variables:

- IELT and PEDT at week 6 of the protocol (halfway point).
- IELT and PEDT at the end of treatment.
- IELT and PEDT three months after finishing the protocol.

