### Data Analysis Plan

A descriptive analysis will be performed of the sociodemographic and clinical characteristics of the research subjects. For the categorical variables, absolute and relative frequencies will be estimated. For the numerical variables, central tendency and dispersion measurements will be estimated.

To evaluate the efficacy of this new therapy, the proportion of patients whose illness improves will be estimated and compared with the expected proportion proposed by the hypothesis (30%). Improvement is defined as the tripling of the baseline (without treatment) intravaginal latency time.

The safety will be evaluated by estimating the incidence of adverse events experienced by the patients during the study. These will be classified by the degree of severity according to WHO criteria.

The analyses will be performed with Stata 14.

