## **Data Collection and Processing Techniques and Procedures**

The patients are admitted to the clinic where they receive a medical evaluation in which they are diagnosed as patients with primary PE. Once this occurs, they are invited to participate in the study by their own voluntary choice. If the patient is interested in participating, the informed consent process is conducted and the corresponding document is signed. Then, an informational email is sent to the telephone center staff responsible for investigations, so that the information required from the patient is inputted into the corresponding database for the purpose of following-up on all of the therapy and follow-up appointments.

Prior to receiving therapy, the patient will perform a two-week process in which he will measure the intravaginal latency time with a digital timer or stopwatch APP and record it on the in-home chart. This has two objectives: first, the patient adapts to the way in which he will measure this time when having sexual relations during the study; second, to have a more precise reference point for the initial IELT, which will be used as a baseline to demonstrate changes during the study protocol.

The therapy will be conducted as follows: Three (3) sessions per week for twelve (12) consecutive weeks, with a duration of 30 minutes each, with the application of 20 Hertz with a pulse amplitude of 200 MI sec. in each session. The intensity will be applied individually for each patient depending on the tolerance of the individual. In each session, it is normal to have plantar flexion of the foot and flexion of the first toe, and after the session and particularly during the first sessions there is the possibility of muscle pain, which should be tolerable. Appendices 3 and 4 provide a more detailed description of the scheme and procedure.

During the study, each patient will have an in-home chart which he must fill out after each sexual encounter and bring to each appointment. The patients will be given strict telephone follow-up calls aimed at their keeping their monthly follow-up appointments, or if not possible due to lack of time a virtual appointment will be conducted by the physician using skype or by telephone.

It is essential that each patient who is admitted into the study complies with the scheduled electrostimulation sessions. If one of the protocols is broken, the patient will be treated as a loss to follow-up since his information could be incorrect.

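### A man who starts other premature-ejaculation treatment after enrolment would probably drop out of the primary proportion, which raises the single-arm response rate if such men are mainly non-responders

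*Combined protocol and SAP*

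**What the plan says.** Under Exclusion criteria the protocol lists "Use of treatment for premature ejaculation during the study or over the 6 months prior to beginning the study". A separate bullet excludes men "Taking medications that affect ejaculation control, including psychiatric medications, opioid analgesics and medications for pathologies of the prostate such as alpha blockers". The Sample section defines the sample as "Patients in the study population who meet the following selection criteria", so these bullets decide who belongs to it.

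Three other places bear on a man who starts such treatment after enrolment.

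- Data Collection and Processing Techniques and Procedures: "If one of the protocols is broken, the patient will be treated as a loss to follow-up since his information could be incorrect". The sentence before it concerns attendance at stimulation sessions.
- Sample size: 18 men are needed, and "After adjusting this number by a percentage of loss of 30%, which is observed in daily practice, 24 patients will be included".
- Data Analysis Plan: the proportion improved is compared with 30%. No denominator, analysis set or missing-data rule is given.

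The Primary Outcome is the proportion who triple their baseline latency time (IELT), "as measured by the IELT (intravaginal ejaculation latency time) during the therapy and three months after completion". The last assessment listed under Outcome Variables is "IELT and PEDT three months after finishing the protocol".

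**The concern.** An exclusion criterion should describe a man at entry. Use of other treatment during the study happens afterwards, and it may happen because stimulation has not worked. The Theoretical Framework says that drugs for this condition give good results, so a man without benefit has a plausible reason to start one. The reason is strongest in the three months after the last session, when stimulation has ended and the primary outcome is still open.

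If such a man is taken out, the denominator shrinks by someone who would probably have counted as a failure, and the reported proportion rises. In a randomised trial a control group might share part of that distortion. Here one proportion is set against a fixed value, so any distortion goes straight into the result. No material effect is claimed at week 6 or at the end of treatment.

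**Working it through.** **Which handling the text points to.** The exclusion bullet bars use during the study, and the Sample section defines the sample by the bullets. The loss rule removes men whose information could be incorrect, a reason that fits latency measured on a drug. The step from 18 to 24 provides for men who do not count towards the 18. Together these point to removal. Two links are implicit: the loss rule sits beside a sentence on session attendance, and nothing says whether a loss leaves the denominator or counts as a failure.

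**The plan's own figure.** Inputs from Sample size: P0 = 10%, P1 = 30%, alpha 5% (taken as one-sided), and a stated beta of 80% read as 80% power. The normal-approximation formula is

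n = [(z_alpha √(P0(1−P0)) + z_power √(P1(1−P1))) / (P1−P0)]² = [(1.645 × 0.300 + 0.842 × 0.458) / 0.20]² = 19.3, so 20.

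This is close to the stated 18. The loss step reproduces as 18 × 1.30 = 23.4, so 24.

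**Effect of removal.** Assumptions, since the documents give no counts: 24 enrolled, 5 of whom triple on stimulation alone, and starters who are all failures. The p-value is the exact one-sided binomial P(X ≥ 5 | n, 0.10). The cut-off is the smallest responder count with p ≤ 0.05.

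| Starters removed | Rate | p against 10% | Cut-off | Gap to 30% (points) |
|---|---|---|---|---|
| 0 | 5/24 = 20.8% | 0.085 | 6 | 9.2 |
| 3 | 5/21 = 23.8% | 0.052 | 6 | 6.2 |
| 4 | 5/20 = 25.0% | 0.043 | 5 | 5.0 |
| 7 | 5/17 = 29.4% | 0.022 | 5 | 0.6 |

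Seven is the 30% loss allowance applied to 24 (0.30 × 24 = 7.2), an extreme in which every loss is a failing starter. If the true rate is 10% and four non-responders are always removed, success needs 5 of 20 instead of 6 of 24. The chance of false success then rises from 0.028 to 0.085.

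**Where the effect stops.**

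- With 1 to 3 removals the cut-off stays at 6, so no decision changes.
- With 4 responders, p falls from 0.214 (4/24) to 0.133 (4/20) and 0.083 (4/17), never below 0.05.
- With 6 responders, 6/24 already gives p = 0.028. So with up to seven removals, the exact test changes its answer only with exactly 5 responders and at least 4 failing starters.
- Break-even with 4 starters is 4 × 5/24 = 0.83 responders among them. One gives 4/20 = 20.0%, almost no bias. Two give 3/20 = 15.0%, below 20.8%.
- The exact test is my choice. By the normal approximation the cut-off at 24 is 24 × 0.10 + 1.645 × √(24 × 0.10 × 0.90) = 4.82, so 5 of 24 would already pass and four removals would change nothing.
- Against 30%, P(X ≤ 5) is 0.229 at n = 24 and 0.416 at n = 20. Neither is small, so only the estimate moves.

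**The case against.** The strongest reply is that the plan already covers the case. Other treatment is barred, using it breaks the protocol, and a man who breaks the protocol is a loss because his data may be wrong. That reading is fair, and it is the one adopted here. It does not answer the point, because removal is the handling that can bias the rate.

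A reader might infer that the plan is silent on such a man, or that his on-drug latency would be kept and the drug's effect credited to stimulation. The documents do not support either. The loss rule plausibly reaches him, its reason argues against keeping his measurements, and no section proposes keeping them.

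Three further objections stand in part.

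- An analysis of evaluable patients is defensible in a phase II trial meant to lead to comparative studies. But then the rule and the denominator should be written down, and the rate with starters counted as failures shown beside it.
- The undefined denominator affects every loss, including missed sessions. That is true, and the fix below settles only the starters. They deserve their own rule because their departure may be a consequence of failure.
- The size depends on chosen counts, and the crossing of 0.05 uses a test against 10% that the Data Analysis Plan does not describe. Both are correct and limit the claim.

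**Conclusion.** The point holds as a probable bias of unknown size. As written, the plan most likely removes men for something they do after enrolment, and that raises the response rate if they are mainly non-responders. In the illustration the rise is 25.0% − 20.8% = 4.2 percentage points for four failing starters. It rests on assumed numbers of starters and responders, on the starters being failures, and on losses leaving the denominator.

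A reader might infer that the trial would reach a false positive conclusion. The documents do not support that. The change of decision needs a narrow set of counts and an exact test against 10%, and the comparison actually written, with 30%, shows no change beyond the estimate. The plan should still be changed, because the correction is cheap and the choice should not be left until results are known. Confidence is medium.

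**What to change.** 1. Exclusion criteria: limit the bullet to use at entry or in the prior 6 months. Keep other treatment prohibited through the three-month assessment as a conduct rule.
2. Primary Outcome and Data Analysis Plan: add that a patient who, after enrolment, starts any other premature-ejaculation treatment, or a drug that affects ejaculation control, remains in the denominator. He counts as a non-responder at each assessment from that date; earlier assessments stand as measured.
3. Data Collection and Processing: state that this is not a loss to follow-up.
4. Ask about such use at the week-6, end-of-treatment and three-month assessments, and record product and start date. The in-home chart (Appendix 2) is not in the supplied text, so it may already have a place for this.
5. Report two sensitivity rates: starters removed, and starters kept with latency as measured.

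The cost is a few sentences, one question at existing assessments, perhaps a chart column, and two extra rates. The main rate may be lower. Each true responder who starts a drug, even for an unrelated reason, becomes a failure and costs 1/24 = 4.2 points. With two such men among five responders the rule gives 3/24 = 12.5%, further below 20.8% than the 15.0% from removing all four starters. The sensitivity rates would show this.
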